This study, encompassing both phases one and two, utilizes a one-armed, within-subjects design and will run for roughly 24 total months. Youth subjects will receive the intervention (YST+YM) and will each be assessed at 4 timepoints: prior to initiating intervention (baseline, week 1), the intervention midpoint (week 6-7), the conclusion of the intervention (post-test, week 12), and then 3 months after the intervention concludes (follow-up, 24 weeks). Adult support team members will be assessed only at post-test (week 12).

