5. SUBJECT POPULATION

Number of Subjects: This study includes three sets of subjects, including (1) youth patients, (2) parents, and (3) their respective adult support team members. The subject population is the same for both phases one and two.

• Youth patients: We will enroll approximately n = 60-70 total adolescent patients in the Child and Adolescent Partial Hospitalization Service (CAPHS). The first n = 5-10 of these will be used to refine and optimize the feasibility and acceptability of YST+YM. All

Page 4 of 64 Version Date: 12/13/21 subjects will be used to evaluate target engagement. Based on consultation with CAPHS clinical director, [name] (LMSW-R), greater than 80% of patients are expected to be eligible for participation. Of eligible patients, roughly 50% are estimated to enroll in the study. Again based on consultation with [name], 75% of the initially enrolled patients are expected to complete the study. Thus, we will screen approximately 165 patients to identify 130 eligible subjects, of which 65 are expected to enroll. Given low attrition for comparable clinical programs in CAPHS (i.e., a year of pilot implementation of traditional YST in that clinic), we conservatively estimate a 25% attrition rate. Attrition will be handled with an intent-to-treat design. Given these considerations, we anticipate n = 50 subjects will provide follow-up data, providing a sufficient sample size to detect a signal for intervention target engagement.

- Parents / legal guardians: We will invite one parent / legal guardian per enrolled youth to provide feedback on the intervention, proxy-ratings of the youth's emotional well-being, as well as self-report of their own well-being. Based on consultation with clinic staff who regularly interact with this population, recruitment and retention rates for parents are expected to be roughly 80% per youth who completes the study. Thus, for the roughly n = 50 youth subjects who provide full follow-up data, we expect roughly n = 40 parents / guardians to complete all measures. This is a sample size sufficient to refine the intervention with informal feedback and to further evaluate target engagement as assessed by proxy-report.

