Teen	 Child pre- screening (with therapist) Consent & contact information Adult team pre- screening & nominations Social & emotional survey Interactive Session 1 (only teen) 	 Weekly texts Weekly contact with support team 	 Weekly texts Weekly contact with support team Social & emotional survey Interactive session 2 (can bring adult team members) 	 Weekly texts Weekly contact with support team 	 Weekly texts Weekly contact with support team Social & emotional survey Interactive session 3 (can bring adult team members) Feedback survey & semi- structured interview 	 Social & emotional survey Feedback survey & semi- structured interview
Parent / Guardian	 Consent & contact information Adult team pre-screening & nominations 	 Adult experience and feedback survey 			 Adult experience and feedback survey 	
Supportive Adults	Consent & contact information	 Adult experience and feedback survey Education session Weekly contact with teen Weekly phone check-ins with study staff 	 Weekly contact with teen Weekly phone check-ins with study staff Some adults also receive weekly texts with teen 	 Weekly contact with teen Weekly phone check-ins with study staff Some adults also receive weekly texts with teen 	 Adult experience and feedback survey & semi- structured interview Weekly contact with teen Weekly phone check-ins with study staff Some adults also receive 	

		weekly texts with teen	

Table 2. Study measures and their contents

Measure Group	Contents			
Child pre-screening Format: staff-administered Recipients: referring therapist Administered (1x): Prior to assent / consent Approx. duration: 5 mins	 Inclusion / Exclusion: Custom questions designed to evaluate whether youth meet criteria to participate in the study (see criteria above). 			
Adult support team member pre-screening Format: staff-administered Recipients: youth and consenting parent/guardian Administered (1x): Prior to consent Approx. duration: 5 mins	 Inclusion / Exclusion: Custom questions designed to evaluate whether youth-nominated adults are appropriate for joining the youth's support team. 			
Contact information Format: staff-administered Recipients: All Administered (1x): After consent Approx. duration: 5-10 mins	 Personal contact information (e.g., phone, email) Youth only: emergency information and pre-existing suicide safety plan for youth subjects (acquired from youth's current therapist) 			

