Adult experiences and feedback survey Format: Self-report	 Identity confirmation: Name and date of birth for longitudinal linking survey linking in database Demographics (e.g., age, race, gender) Acceptability ratings and feedback: Custom rating scales and open-ended questions about intervention 			

Recipients: Parents, adult supports Administered (2x): After first session, Weeks 10-12 Approx. duration: 15-20 mins	 acceptability, time taken, and perceived benefits for child Child depression symptoms: PROMIS Parent Proxy Short Form v2.0 - Depressive Symptoms 6a Child life satisfaction: PROMIS Parent Proxy Short Form v1.0 - Life Satisfaction 4a Adult depression symptoms: PROMIS Short Form v1.0 - Depression 4a Adult general stress: NIH Toolbox Perceived Stress Fixed Form Age 18+ v2.0
Youth social and emotional survey Format: Self-report Recipients: Youth only Administered (4x): During the three intervention sessions, follow-up (week 22-24) Approx. duration: 30-60 mins	 Identity confirmation: Name and date of birth for longitudinal linking survey linking in database Demographics (e.g., age, race, gender) Acceptability ratings and feedback: Custom rating scales and open-ended questions about intervention acceptability and perceived benefits. Depressive symptoms: PROMIS Pediatric Short Form v2.0 - Depressive Symptoms 8a Suicidal thoughts and behaviors: Short Mood and Feelings Questions about recent and historic suicide attempts Social Connectedness: Interpersonal Needs Questionnaire – Belongingness subscale Feelings of meaning and purpose: Claremont Purpose Scale – Goal-directedness and Personal Meaning subscales Emotion Regulation: Interpersonal Emotion Regulation Questionnaire - Social Modeling Subscale, Difficulties in Emotion Regulation Scale – Regulation Strategies Subscale Engagement with healthy activities: Behavioral Activation for Depression – Short form – Activation Subscale Adult support team activities: Custom questions about frequency of contact with parents and team adults on intervention support team. Questions include content about different activities (e.g., help with homework, social support) and forms of interaction (e.g., in person, over the phone).

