Youth-focused Module (YM): The YM consists of three remote sessions involving the youth and 12 weekly text message prompts encouraging the subject to reflect on their usage of content from the YM. The first session occurs before discharge and will be either in-person or remote, depending on current clinic policy and patient/interventionist availability. The first session includes only the patient and the interventionist. The second (post-discharge weeks 4-6) and third (post-discharge weeks 10-12) sessions happen after discharge and will all be remote. For these post-discharge sessions, youth subjects will also be encouraged, but not required, to invite one or more members of their support team. The YM content is strengths-based and centers on seeking social connection, emotional balance, and purpose/meaningful activities. [name] will supervise the treatment through regular review of audiotapes (random sample of 20% of sessions) to ensure fidelity.

Page 15 of 64 Version Date: 12/13/21 • Text Messages: Subject identifying information, clinical symptoms (including suicide risk) and PHI is not exchanged in the text messages themselves. Detailed information about text messaging is included under the "Privacy and Confidentiality of Subjects and Research Data" section. Privacy and security risks associated with text messaging are described in detail to all subjects during assent / consent, including the inherent unprotectability of text-message data and the option to automatically withdraw from texts at any time with the phrase "unsubscribe".

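### Parent proxy ratings are offered as evidence on target engagement, but they start after session 1 and measure no Aim 2 target

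*Combined protocol and SAP*

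**What the plan says.** Section 5 (Parents / legal guardians) invites one parent per youth to give, among other things, "proxy-ratings of the youth's emotional well-being". It expects about 40 parents to complete all measures and calls this enough "to further evaluate target engagement as assessed by proxy-report".

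Table 2 in section 9 schedules the adult survey as "Administered (2x): After first session, Weeks 10-12". Its child-proxy content is "Child depression symptoms: PROMIS Parent Proxy Short Form v2.0 - Depressive Symptoms 6a" and the PROMIS parent-proxy life satisfaction form (4a). The other standard scales in that survey measure the adult's own depression and stress.

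In Table 1 the parent's pre-discharge cell holds only consent, contact details and team nominations. The "Adult experience and feedback survey" first appears under post-discharge weeks 1-3 and again under weeks 10-12. On the youth module, section 9 states: "The first session occurs before discharge".

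The Aim 2 hypotheses in section 2 concern contacts the youth initiates with supportive adults, interpersonal emotion regulation and perceived social support. Section 4 adds connectedness. Sections 2 and 4 both class depression as a distal target. Section 17 names no parent-reported outcome.

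**The concern.** The trial has one arm, so change from baseline is the only comparison it offers. A rating first taken after the intervention has begun is not a baseline, and any change before it cannot be recovered later. Separately, a scale can support a claim of target engagement only if it measures a target. As written, the plan invites a fall in proxy-rated depression between weeks 1-3 and weeks 10-12 to be reported as target engagement. In fact it would be a partial estimate of a distal outcome. The Aim 3 estimates are meant to inform later trials, so a truncated informant estimate would also be less useful there.

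**Working it through.** **The plan's own figure.** Section 5 expects 65 youths to enrol with 75% retained: 65 × 0.75 = 48.75, stated as about 50. At 80% parent participation, 50 × 0.80 = 40 (or 48.75 × 0.80 = 39). The parent number reproduces. The difficulty lies in when these parents are asked and what they are asked.

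**Timing.** Three places agree.
- Section 9, youth module: session 1 is before discharge.
- Table 2: the adult survey follows the first session.
- Table 1: parents have no survey before discharge, and their first falls in post-discharge weeks 1-3. Youths already have weekly texts and team contact in that column.

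If the first session in Table 2 means the adults' education session, the conclusion is the same, because that session is itself part of the intervention. Support-team adults, who receive the same survey, are also first surveyed in weeks 1-3 by Table 1. Section 4 says they are assessed only at post-test. On neither reading does an informant rating precede the intervention.

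**Content.**

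| Aim 2 target (sections 2 and 4) | Child-proxy scale in Table 2 |
|---|---|
| Contacts initiated with adults | none |
| Interpersonal emotion regulation | none |
| Perceived support, connectedness | none |

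The two proxy scales map elsewhere. Depression is distal in the plan's own terms, and life satisfaction appears in no aim. A custom item on benefit to the child is listed with the acceptability ratings and is not a target score.

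**Share of change missed.** Take discharge as week 0 and assume linear change up to a final rating at week e. A first rating at week w then misses w/e of the change. The middle of the weeks 10-12 window gives e = 11.

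| First rating | e = 10 | e = 11 | e = 12 |
|---|---|---|---|
| Week 1 | 1/10 = 10% | 1/11 = 9% | 1/12 = 8% |
| Week 2 | 2/10 = 20% | 2/11 = 18% | 2/12 = 17% |
| Week 3 | 3/10 = 30% | 3/11 = 27% | 3/12 = 25% |

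The interval between the two ratings can range from 10 − 3 = 7 weeks to 12 − 1 = 11 weeks, so parents' change scores would not cover the same period.

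**Sensitivity to shape.** Suppose instead that change is front-loaded, following g(t) = 1 − 2^(−t/3), with e = 12. The share missed is g(w)/g(12), where g(12) = 0.9375. This gives 0.206/0.9375 = 22%, 0.370/0.9375 = 39% and 0.500/0.9375 = 53% for weeks 1, 2 and 3. If nothing changed until after week 3, nothing would be missed. The documents give no basis for choosing among these shapes.

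**The case against.** The best defence is that little hangs on these data. Section 5 offers them as a further look, describes them openly as ratings of emotional well-being and names no aim. The plan also uses the word target, qualified as distal, for depression. On that view the fault is one loose phrase in a sample-size paragraph. This is fair as to seriousness. But section 4 separates intervention targets from distal ones, and the term target engagement belongs to Aim 2, so the phrase still needs correcting.

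On timing, the survey window opens in post-discharge week 1, and section 4 labels the youth baseline itself as week 1. All that must come before a week-1 rating is one session with the youth alone. The section on subject withdrawals allows two weeks after discharge to confirm even one supportive adult, so some teams may barely have started. This stands: it is a late baseline of variable timing, and the loss need not amount to weeks of intervention for every youth.

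Three stronger readings are tempting and are not supported.
- A reader might infer that this survey is the only source on youth change other than self-report. It is not. Section 17 models text response rates, Table 2 lists a staff-administered C-SSRS, and support-team adults receive the same survey.
- A reader might infer a definite loss of power. Section 17 specifies no test on parent data, its power statement concerns the Aim 2 mixed models, and it treats Aim 3 as purely descriptive. Any power figure would need a test and a correlation that the plan does not supply for these ratings.
- A reader might infer that Aim 2 itself fails. Section 4 schedules a youth assessment before the intervention, and the youth survey carries the Aim 2 measures.

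**Conclusion.** Both parts hold on the text. No informant rating of the youth precedes the intervention, and no Aim 2 target is rated by proxy, so section 5's statement has no matching instrument. Section 17 gives it no analysis either. Under linear change to week 11, the late start misses about 9% to 27% of the change, depending on whether the first rating falls at week 1 or week 3. That range rests on the assumed shape: early change would make it larger and delayed change smaller. The timing and content findings need no such assumption. The main Aim 2 analysis, based on youth self-report, is unaffected. The change is worth making because a missed baseline cannot be collected afterwards and the remedy is small.

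**What to change.** 1. Give the two child-proxy forms at the pre-discharge consent session, after the parent has consented and before session 1, and again at weeks 10-12. Reading 6a and 4a as item counts, this is 6 + 4 = 10 items. Section 9 schedules the baseline session only after consent and nominations, so the order already allows it. Amend Tables 1 and 2 to match.
2. Leave the acceptability items after session 1, where they belong.
3. Reword section 5 so that proxy depression and life satisfaction are distal (Aim 3) outcomes and not evidence of target engagement.
4. List both among the Aim 3 descriptive estimates in section 17.

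The cost is a few extra minutes for parents (an assumption; the documents give no time for these forms alone) at a session they already attend, plus wording changes. There is no new visit and no change in sample size. Keeping the present claim in section 5 would instead require a proxy measure of an Aim 2 target, which is a larger change.

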4. STUDY DESIGN

This study is a two-phased, one-armed pilot trial to evaluate feasibility, acceptability, and target engagement of YST+YM. It will also facilitate estimation of clinical outcome prevalence, including suicidal ideation and attempts over the intervention period and through post-intervention follow-up.

In phase one (content refinement; n = 5-10), feasibility and acceptability will be optimized via measures of subject engagement with the intervention (i.e., text-message response rates) and with subject feedback during semi-structured interviews. We will also assess feasibility of the assessments used to measure emotion regulation, perceived social support and connectedness, and clinical outcomes (i.e., anxiety, depression, and suicidal ideation and attempts).

In phase two (pilot; n = 60-70), target engagement and prevalence of clinical outcomes will be addressed, as well as continued assessment of feasibility and acceptability of YST+YM. Consistent with specific aims above, intervention targets include engagement with treatment (i.e., initiating contact with support team members), changes in emotion regulation skills, and perceived social support and connectedness. Distal targets, including anxiety, depression, and suicidal ideation and attempts will also be assessed to establish point estimates for power analysis and sample size planning in future trials. Subject engagement with the intervention and feedback during semi-structured interviews will be used to assess feasibility and acceptability of YST+YM (following initial modification in response to phase one subject feedback).

Because the intervention lasts approximately three months per subject, the phases will be staggered, such that some subjects will be enrolled in phase two before all phase one subjects have completed their entire intervention course. For example, we anticipate that n = 5-10 phase one subjects may complete the first remote session of YST+YM within 6 weeks of the study start date. Because we collect feedback immediately following each session, this means we will have received all the information required to finalize that session's outline and content for the launch of phase two – even though these phase one subjects will have several weeks left of YST+YM overall.

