Refinement phase versus pilot phase: *All subjects in all phases will complete the same procedures and will receive a brief semi-structured interviews to assess acceptability and appeal of the intervention.* In phase 1 (content refinement), feedback from the first N = 5-10 youth subjects and their supportive adults (estimated N = 15-20) will be used to refine YM content. Note, the YM text messages will also be refined using any available input from a related text message pilot study (STUDY00006613). In phase 2 (pilot), all remaining subjects will receive the refined content that was updated with feedback from phase 1 subjects. Note, the broader and previously validated YST intervention will not be modified; only the novel YM being added to it in this study will be modified after patient feedback. Post-feedback refinements will be limited to streamlining improvements (e.g., better phrasing of text messaging, more intuitive examples for one-on-one sessions). The overarching themes and structure of the YM will not be edited without submission and approval of a written revision to this protocol (e.g., content will stay focused on connection, emotional balance, finding goals and purpose - promoted by three sessions across 12 post-discharge weeks).

COVID-19 Re-boot Guidance Information

Study staff will follow all COVID-19 reboot guidelines for safe conduct of research, per the URMC Guidance for Human Subject Research website. The PI and staff will remain vigilant about any further changes that need to be made to study procedures if there are changes to the research reboot guidance. URMC guidelines:

https://www.urmc.rochester.edu/coronavirus/coronavirus-research/guidance-for-researchers/human-subjects-research.aspx

Research results will not be provided back to the subject.

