17. DATA ANALYSIS PLAN

For Aim 1, we will use descriptive statistics to gauge achievement of feasibility and acceptability thresholds for patients. Means above 3.5 (on a 5 point scale) will be regarded as adequate feasibility and acceptability.

For Aim 2, a linear mixed effects model will be used to evaluate (a) overall frequency of responding to text messages and (b) trends in text response rates over time. Aim 2 will also utilize generalized linear mixed effects models (fixed effect for time, with a random effect for individual) to evaluate changes in intervention target scores over time. Each of the intervention targets will serve as the outcome variable in its own separate model.

For Aim 3, means and proportions will be estimated and retained for future study planning.

A power analysis evaluating these models was conducted via simulation. For the linear mixed effects models (Aims 2), assuming a moderate effect size (d = .50) and moderate within-subject shared variance attributable (ICC = .05), simulations show this model will have adequate power (.82) to detect target engagement over the course of the intervention. Because Aims 1 and 3 utilize only descriptive statistics and require no statistical inference, no power analysis was conducted.

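### Youths who receive the module before refinement are included in target engagement, the 3.5 adequacy rule is not limited to the refined module, and the sections disagree on whether 60-70 is the total or the phase-two number.

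*Combined protocol and SAP*

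**What the plan says.** All references are to the combined protocol and SAP.

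- **Content by phase (section 9, refinement versus pilot phase).** Feedback from the first 5-10 youths and their adults is used to revise the youth module. Then "In phase 2 (pilot), all remaining subjects will receive the refined content that was updated with feedback from phase 1 subjects". The same paragraph leaves the established support-team component unchanged, limits revisions to streamlining (text phrasing and session examples are its instances), and requires a protocol revision before themes or structure can change.
- **Who is analysed (section 5).** "We will enroll approximately n = 60-70 total adolescent patients", and "The first n = 5-10 of these will be used to refine and optimize the feasibility and acceptability of YST+YM". All "subjects will be used to evaluate target engagement".
- **Who is analysed (sections 1 and 4).** Section 4 reads "In phase two (pilot; n = 60-70), target engagement and prevalence of clinical outcomes will be addressed", and section 1 gives the same number for phase two. Section 4 also describes the phase-two acceptability assessment as coming after the phase-one modification.
- **Analysis (section 17).** "Means above 3.5 (on a 5 point scale) will be regarded as adequate feasibility and acceptability". No phase is named. The Aim 2 models contain time and a random effect for the individual, with no term for phase or content version. Frequency and trend of text responses are also Aim 2 analyses.

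**The concern.** The design has two steps: improve the module, then test the improved module. For the second step, the youths who matter are those who received the improved content. As written, the youths on whom the content was tuned are also in the target-engagement analysis, and nothing keeps their ratings out of the 3.5 decision. The ratings that prompted a repair could then help decide whether the repaired module is adequate.

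Text response is the Aim 2 outcome most directly exposed, because message wording is one of the things that may be revised, partly from a separate text-message pilot.

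The sections also disagree on numbers. If 60-70 is the total, phase two has fewer youths than sections 1 and 4 say. If it is the phase-two number, section 5's recruitment figures fall short. A reader cannot tell which sample the power statement or the report will use.

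**Working it through.** **1. Share of youths on the earlier content.** Taking section 5's total: 5/70 = 7.1% to 10/60 = 16.7%.

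**2. The two readings of 60-70.** As a total, phase two holds 60 - 10 = 50 to 70 - 5 = 65 youths. As the phase-two number, the total is 60 + 5 = 65 to 70 + 10 = 80. Section 5's recruitment line ("of which 65 are expected to enroll") fits the first reading.

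**3. The 3.5 rule.** Pooled mean = w × m1 + (1 - w) × m2, where w is the phase-one share and m1, m2 are the phase-one and phase-two mean ratings. The documents give no ratings, so m1 is assumed. The table shows the m2 at which the pooled mean equals 3.5, that is (3.5 - w × m1)/(1 - w).

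| Assumed m1 | 5 of 70 | 10 of 60 |
|---|---|---|
| 2.5 | 3.58 | 3.70 |
| 3.0 | 3.54 | 3.60 |
| 4.5 | 3.42 | 3.30 |

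Pooling can therefore move the decision either way. With m1 = 3.0 it changes only if the phase-two mean lies between 3.50 and 3.54 (5 of 70) or 3.50 and 3.60 (10 of 60). For example, m2 = 3.55 gives (5 × 3.0 + 65 × 3.55)/70 = 3.51, which still passes, but (10 × 3.0 + 50 × 3.55)/60 = 3.46, which fails.

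**4. Dilution of the Aim 2 effect.** Pooled d = w × d1 + (1 - w) × d2. Take d2 = .50 (section 17's value) and assume d1:
- d1 = .20: .479 (w = .071) to .450 (w = .167)
- d1 = .25: .482 to .458
- d1 = 0: .464 to .417

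**5. The plan's power figure.** Section 17 gives .82 for d = .50 and ICC = .05, without N, alpha or sidedness. Assume two time points, a random intercept and two-sided alpha .05. The noncentrality is d/√(2(1 - ICC)/N). At N = 65 this is .50/√(1.90/65) = 2.92, and power is .821, which reproduces .82. The match is not unique: N = 50 one-sided gives .812.

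**6. Phase two alone.** Dropping 5-10 of 65 leaves 55-60.

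| | N = 65 | N = 60 | N = 55 |
|---|---|---|---|
| Two time points | .821 | .789 | .752 |
| Three time points (weeks 0, 6, 12) | .827 | .796 | .760 |

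Section 5 also says "we conservatively estimate a 25% attrition rate". If only completers are analysed, the two-point figures are .701 (pooled, 49), .663 (45) and .620 (41).

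**7. Could a phase-by-time test detect a version difference?** Take a difference in d of .50 - .20 = .30, with standard error √(1.90 × (1/n1 + 1/n2)). For 5 versus 65 the standard error is .640 and power is about 7%. For 10 versus 50 it is .477 and power is about 9%.

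**8. Does phase identify content version?** Not reliably. Section 4 staggers the phases and finalises content session by session. Session 3 falls in post-discharge weeks 10-12 (section 9), and youths have 14 weeks to complete all sessions (section 15, Subject Withdrawals). A phase-two youth discharged less than 14 - 10 = 4 weeks after the last phase-one youth could reach session 3 first.

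**The case against.** The strongest reply is that the two versions are close to identical by design. The support-team component is fixed, themes and structure are fixed, and only phrasing and examples may change. Pooling them, with at most one youth in six on the earlier content, is a defensible choice in a one-armed pilot. This stands, and it limits how much weight the point can carry. It does not remove the point, because phase one exists to improve feasibility and acceptability, and the 3.5 rule measures exactly those.

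A second reply is that no section says the ratings are pooled across phases, and section 4 already places the phase-two acceptability assessment after modification. This also stands. A reader might infer that the plan pools the ratings; it is only silent on the set, whereas pooling for target engagement is explicit in section 5.

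Third, the rating illustration sits close to the cut-off. With an assumed rating SD of 1, the standard error of a 50-youth mean is 1/√50 = 0.14, wider than either window in step 3 for a phase-one mean of 3.0. The example shows that a flip is possible, not that it is likely.

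A reader might also want a phase-by-time term to show whether refinement worked. With 5-10 phase-one youths, and content version possibly changing within a youth, such a test would tell almost nothing.

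**Conclusion.** The point holds as a mismatch between the stated design and the analysis, with a probably small numerical effect. Section 5 conflicts with sections 1 and 4 on who is in the target-engagement analysis and on what 60-70 counts, and section 17 does not settle either matter. Phase one is 7%-17% of youths. With effects of .20 and .50 assumed before and after refinement, pooling lowers d by .02-.05. The 3.5 decision changes only when the phase-two mean is near the cut-off. Acceptability ratings and text response rates matter most.

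A reader might infer that pooling invalidates the target-engagement result, or that it spoils both steps of the design. The documents do not support that. Refinement relies on interviews, ratings and text responses gathered as the study proceeds, which pooling the final models does not affect, and the permitted changes are narrow.

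The ratings, the phase-one effect sizes and the rating SD are assumptions. So are alpha, sidedness and the number of time points in the power check.

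**What to change.** 1. In section 17, apply the 3.5 rule to phase-two youths and report phase-one ratings separately as refinement data.
2. Keep the pooled Aim 2 models as planned. Report the phase-two-only change and text response rate beside them, and base statements about the refined module on the phase-two estimate. Do not rely on a phase-by-time test.
3. Record the content version delivered at each session, for description only.
4. Reconcile sections 1, 4 and 5 so that 60-70 is either the total or the phase-two number, and give the N, alpha and sidedness behind the .82.

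The cost is wording and one data field. The phase-two estimate rests on 5-10 fewer youths, with power of about .75-.80 instead of .82 at 65 enrolled under the step 5 assumptions (two or three time points). The pooled estimate is kept. Limiting the 3.5 rule costs no power, because Aim 1 is descriptive.
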